# **Revision of primary arthroplasty:**

Patients who have their primary arthroplasty (Bi-UCKA or TKA) revised will continue to be followed up at scheduled study time points. Information regarding the type of revision surgery will be recorded in the CRF. Data from any patients who are revised will not be included in the overall study analysis after the point of revision. However, data will continue to be collected in order that an assessment of the morbidity associated with revision arthroplasty can be made.

# 14. Definition of End of Trial

The trial will end on the date that the final follow-up visit for the last patient occurs.

# 15. Sample size

The primary outcome measure is proportion of patients in each arm with a bi-phasic (normal) gait. 23% of TKA patients have a bi-phasic gait after surgery compared to 70% of UKA patients. Bi-UCKA surgery is unlikely to achieve quite the same level as UKA, nevertheless it is anticipated that a substantial proportion of this effect should be achievable. We therefore believe that 60% of Bi-UCKA patients might have a normal bi-phasic gait after surgery. To detect a difference of this size with a power of 90% at a 5% level of significance using a chi-squared test we would need to study 36 patients per group (calculated using 'sampsi' in Stata 11.2 without continuity correction). We will allow an additional 10% for loss to follow up at 1 year and will therefore study 40 patients per group (80 in total) recruited over 41 months. All patients will be recruited at Glasgow Royal Infirmary and will be operated on by one of three surgeons and randomisation will be stratified by surgeon. It is expected that each surgeon will conduct roughly similar numbers of operations, in both randomised groups. We will adjust for any clustering generated within surgeon by fitting surgeon as a random effect, and would expect to recover and possibly have a net increase in power by adjusting for pre-specified baseline covariates that would be strongly associated with 1 year outcome.

# 16. Statistical analysis

All statistical analyses will be governed by a comprehensive Statistical Analysis Plan, which will be agreed by the research group and approved by the independent Data Monitoring Committee. The primary outcome (at 1 year) will be analysed according to the intention to treat principle, and will use a mixed effects logistic regression model, with surgeon fitted as a random effect. We will also consider a per protocol analysis, including those who received the surgery as intended. We would adjust this primary analysis for baseline gait i.e. the primary outcome measured at baseline. At present there are no subgroup analyses proposed for the primary outcome.

Analysis of secondary outcomes will be similar to that for the primary outcome, except using generalised linear models appropriate to the distribution of the specific outcome (e.g. linear or logistic). At present there are no count data (e.g. Poisson or negative binomial regression) or time to event outcomes (e.g. Cox proportional hazards regression) being considered. For the secondary outcomes that have serial measures post randomisation (e.g. 3m, 1 y, 2y, 5y, 10y) we will use repeated measures models to explore any possible time development of a treatment effect we identify.

As indicated above, we will explore the robustness of any findings we report to patterns of missing data, most prominently using multiple imputation models exploring missing data mechanisms assumed to be generated under a 'missing at random' assumption. There will be no formal adjustment for multiple comparisons given the explanatory rather than confirmatory nature of this study.

The independent Data Monitoring Committee will not conduct any formal interim analyses of the efficacy outcomes – their role will be primarily concerning safety.

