In order for patients to be suitable for and benefit from Bi-UCKA surgery they need to have intact Cruciate Ligaments; Douglas et al 2010 demonstrated that 78% of TKA patients have an intact ACL (34). Our own internal audit has revealed very similar rates in our cohort. Exclusions to Bi-UCKA surgery include: absence of cruciate ligaments, flexion contracture >10°, deformities with bone and soft tissue changes that make a compartmental approach to surgery unsuitable. Bi-UCKA could offer significant functional benefits for between 9,000 and 18,000 people in the UK every year who currently receiving TKA for OA of the knee. As Bi-UCKA is tissue preserving it can retain the normal biomechanical function of the knee to a much greater extent and hence may, if carried out accurately using robotic assistance, lead to a better functional and kinematic outcome than is currently achieved with TKA. Figure 4 demonstrates the differences in bone removal between Bi-UCKA and TKA. Bi-UKA surgery may also offer a valuable precursor to TKA surgery particularly for younger patients who are likely to outlive their joint replacement and require revision surgery at a later time point. Conversion from Bi-UKA to TKA in these patients may delay or prevent the need for costly and complex revision TKA surgery.

Figure 4 UKA, TKA and Bi-UCKA radiographs highlighting the difference in bone resection required.

We hypothesise that robotic assisted Bi-UCKA surgery undertaken in appropriately selected patients can offer improved knee kinematics and proprioception in comparison to that afforded by TKA. Furthermore we hypothesise that accurate positioning of implants by robotic assistive technology will improve implant survivorship in Bi-UCKA to the levels achieved with TKA and UKA.

We propose to undertake a randomised controlled trial to compare TKA and robotic assisted Bi-UCKA. We will use a battery of impairment and functional tests to explore the mechanisms underpinning any functional improvements that are observed.

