# **Research Questions:**

- 1. What are the biomechanical kinematic benefits of Robotic Bi-UCKA surgery compared to TKA?
- 2. Are improved knee kinematics and proprioception associated with better clinical and functional outcomes after surgery?
- 3. Is the revision rate after Robotic Assisted Bi-UCKA surgery comparable with TKA surgery?
- 4. Does Robotic Assistance facilitate accurate implantation and alignment of all 4 components of a Bi-UCKA?

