# Secondary Outcome Measures:

- Percentage of patients with a bi-phasic (normal) moment curve during gait (level walking) at two years
- Biomechanical performance–Gait during stair climb/descent and lunge, functional activity assessment (using electrogoniometers).
- Activity Overall daily activity levels, maximum sport/physical activity, functional activity test times (stair climb, timed up and go)
- Impairment Range of motion, proprioception, quadriceps strength (short term outcome) and progression of OA in contralateral knee (long term outcome).
- Clinical Outcomes Clinical knee scores (Oxford Knee Score and New American Knee Society Score, Forgotten Joint Score), pain, analgesic use, complications, implant fixation and satisfaction.
- Safety profile (Determined by revision rate, adverse events, robotic system errors and accuracy of implantation)
- Accuracy of surgical implantation (determined by post-op CT analysis)

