#### 11.2. Assessment of safety

Patient safety will be assessed by comparing complications of surgery / adverse events related to surgery (infection, DVT, PE, delayed discharge from hospital, manipulation under anaesthetic, re-operation and implant survivorship). Safety of the RIO Robotic device will be assessed by recording system errors and malfunctions, as well as by assessing accuracy of implantation.

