# 21. Project timetable: Stages, Go/No-Go Decision Points and Milestones

We have assumed that contracts will be agreed and signed between NHS GGC and DoH by June 2013. We will allow 6 months prior to study initiation in order to obtain appropriate approvals, recruit staff and set up the study. Recruitment will begin in Dec 2013 and will last for 41 months.

Patient follow-up will last 10 years from the time of surgery, meaning that the final patient assessment will be at the end of July 2028. It is vital that patients are followed up for a minimum of 10 years in order to establish long term performance of this novel surgical method. Although we will follow up patients for a 10 year period, the primary knee kinematic data and early surgical outcome data will be collected 1 year after surgery has been completed on each patient. 1 year data collection will be completed by the end of July 2019. We will therefore analyse our 1 year data during August - September 2019 and will aim to have the first sets of publications arising from the study submitted by winter 2019. Subsequent publications will be produced end of 2020 (2 year data), 2023 (5 year data) and 2028 (10 year data).

Critical stages (with Go/No-Go decision points) and Milestones are given in table 2 below.Table 3 contains a gantt chart with key study timelines. A study recovery plan was submitted to the funder to permit the extension of recruitment from a period of 24 months to 41 months. This was granted and the resulting study timeline updates are reflected in Table 3.

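### Section 16 says no time-to-event outcomes are being considered, yet implant survivorship and revision rate over 10 years are stated outcomes; the sentence should be replaced and research question 3 made descriptive

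*Protocol*

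**What the plan says.** Section 16 gives the analysis approach for secondary outcomes. They follow the primary analysis but use "generalised linear models appropriate to the distribution of the specific outcome (e.g. linear or logistic"). It adds that at present no count data "or time to event outcomes (e.g. Cox proportional hazards regression) being considered".

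Five other places treat revision as something that happens over time:

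- Section 4 closes with the hypothesis that accurate robotic positioning "will improve implant survivorship in Bi-UCKA to the levels achieved with TKA and UKA".
- Section 6, research question 3, asks: "Is the revision rate after Robotic Assisted Bi-UCKA surgery comparable with TKA surgery"? No margin, time point or precision target is given.
- Section 10 lists as a secondary outcome: "Safety profile (Determined by revision rate, adverse events, robotic system errors and accuracy of implantation").
- Section 11.2 assesses safety by comparing a list of events that ends with "re-operation and implant survivorship".
- Section 21 justifies the length of the study: "It is vital that patients are followed up for a minimum of 10 years", in order to establish long-term performance.

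Section 13 makes the moment of revision matter for every other outcome as well: "Data from any patients who are revised will not be included in the overall study analysis after the point of revision".

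**The concern.** Survivorship is a time-to-event quantity. An analysis that follows section 16 does not deliver what sections 4, 6 and 11.2 ask for, and one that answers them departs from section 16. This is not detail left to the statistical analysis plan, because the protocol makes a positive statement that points the other way.

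Over 10 years some patients will die or be lost. A yes/no model at a fixed horizon must then drop them, count them as unrevised, or impute an outcome for them. Multiple imputation under missing at random, which section 16 plans for missing data, does not suit a patient who died with the implant in place. Revisions will also be few, so a logistic model may not yield an estimate at all.

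At stake is the long-term safety comparison for a device combination that the synopsis and section 9.1 say is not CE marked for this use. Section 4 itself says that survivorship of non-robotic Bi-UCKA appears poorer than that of TKA.

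**Working it through.** **Inputs.** 40 patients per arm, from 36 evaluable plus 10% loss at 1 year (section 15). TKA survivorship of 98% at 5 years, so 2% revised, and a second TKA figure of just under 3% revised at 5 years (both section 4). The protocol gives no 10-year TKA revision rate, so 5% is an assumption.

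**The plan's own figure.** For gait, 23% against 60%, two-sided 5%, 90% power, no continuity correction:

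n = [1.960 × √(2 × 0.415 × 0.585) + 1.282 × √(0.23 × 0.77 + 0.60 × 0.40)]² / 0.37² = 35.1, rounded up to 36; then 36 / 0.90 = 40.

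The stated 36 and 40 reproduce. They concern gait at 1 year only. Section 15 gives no size or event count for revision and no loss allowance beyond 1 year.

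**Sparse events.** The chance of no revision among 40 TKA patients is (1 − p)^40:

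| Revision rate p | Source | Expected events, 40p | Chance of none |
|---|---|---|---|
| 2% | section 4, 5 years | 0.8 | 0.98^40 = 0.446 |
| 3% | section 4, 5 years (just under) | 1.2 | 0.97^40 = 0.296 |
| 5% | assumed, longer term | 2.0 | 0.95^40 = 0.129 |

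With no TKA events and at least one in the other arm, the logistic odds ratio is infinite. With none in either arm it is undefined.

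**Precision of the comparison.** For one revision in each arm of 40, the Wilson 95% limits for 1/40 are 0.0044 and 0.1288. The Newcombe half-width for the difference is √[(0.025 − 0.0044)² + (0.1288 − 0.025)²] = 0.106, so the interval is −10.6 to +10.6 points. With 0/40 in both arms it is still ±8.8 points. With 36 per arm and one event in each it is ±11.6.

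**What a comparability claim would need.** The protocol states no margin, so margins are assumed here. With equal true survivorship s, one-sided 2.5% and 80% power, n per arm = (1.960 + 0.842)² × 2s(1 − s) / margin²:

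| Survivorship s | 5-point margin | 10-point margin | Exact power at 40 per arm, 10-point margin |
|---|---|---|---|
| 98% | 124 | 31 | 52% |
| 97% | 183 | 46 | 43% |
| 95% | 299 | 75 | 34% |

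The exact column enumerates all outcomes and requires the upper Newcombe limit to fall below the margin. The normal approximation is optimistic with so few events: at 98% and 10 points it gives 89% where enumeration gives 52%.

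**The case against.** The best defence has five parts.

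1. *The statement is provisional.* The sentence opens with a qualifier that limits it to the present, and section 16 puts all analyses under a statistical analysis plan, which is not available here. This stands in part. A reader might infer that survival methods are prohibited, but the text does not go that far. It remains in version 4.2, however, and contradicts the stated outcomes.

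2. *Logistic analysis of revised yes/no is not specified.* Linear and logistic models are given as examples. This stands: that analysis is what section 16 most naturally leads to, not what it prescribes.

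3. *Follow-up is balanced by design.* Visits are fixed (section 11) and reporting is tied to 1, 2, 5 and 10 years after the last patient's surgery (section 23). This stands against a charge of unequal planned time at risk. It leaves death and loss, for which section 16 has only imputation.

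4. *No passage says that a non-significant test will be read as comparability.* This stands. A reader might infer it from question 3, but the protocol calls the study explanatory, claims no power for revision and states no such rule. The gap is only that nothing guards against that reading.

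5. *Survival methods do not create power.* This stands. A log-rank test on a handful of events is as weak as a test of proportions, and a Cox hazard ratio is also non-finite when one arm has no events. The case for Kaplan-Meier or cumulative incidence rests on correct handling of death and loss, and on estimates with intervals.

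It is also tempting to set 98% TKA survivorship against the 88.5% in one cited Bi-UCKA series and treat the 9.5-point gap as the deficit to exclude. The documents do not support that. The first is a 5-year registry average, the second a 6-year figure from a single non-robotic series, and section 4 cites other series from 100% at 4 years to 73% at 10 years.

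**Conclusion.** The concern holds as an inconsistency within the protocol and should be fixed. Section 16 sets time-to-event outcomes aside for now, while sections 4, 6, 10, 11.2 and 21 make revision and survivorship over 10 years part of what the trial is to report. The primary outcome, the randomisation and the sample size for gait are unaffected; one component of a secondary safety outcome is.

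Analysed by logistic regression, the comparison would have a 45% chance of an empty TKA arm at the 2% rate, 30% at 3% and 13% at the assumed 5%, taking all 40 patients as observed. Whatever the model, 40 per arm gives an interval of about ±9 to ±11 points even when the observed counts are equal at zero or one. Comparability could therefore not be shown for a 5-point margin, and only with 34% to 52% power for a 10-point margin, both margins being assumptions. Attrition over 10 years would lower precision further.

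None of this shows that the trial is too small for its purpose or that the investigators intend to claim equivalence.

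**What to change.** **Section 16.** Replace the sentence on time-to-event outcomes. Describe time to first revision by allocated arm with Kaplan-Meier or cumulative incidence estimates, with death as a competing event. Give 95% confidence intervals for each arm and for the difference at 2, 5 and 10 years. Name an interval method that stays defined with no events, because the usual Greenwood variance is zero in that case. No log-rank test, count model or external benchmark is needed. If the statistical analysis plan already does this, only section 16 has to be aligned with it.

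**Section 6, question 3.** Word it as descriptive. State that the trial is not sized to show comparability of revision rates and that a non-significant difference will not be reported as comparability.

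**Data.** Confirm that the CRF records the date of revision. Section 13 mentions the type of revision surgery but does not expressly list the date.

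**Cost.** An amendment to wording and a CRF check, with no new patients or visits. Follow-up runs to 2028, so the change matters most for the 5- and 10-year reports. The downside is a more modest conclusion on revision.

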#### Gait analysis, functional knee assessment and dynamic proprioception:

Biomechanical Gait and Stair analysis will be carried out using our 12 camera VICON Nexus system in the Bioengineering Unit (University of Strathclyde). Gait will be recorded during flat walking, stair ascent/decent and lunge movements allowing comparison between the two

surgical treatment options. We will also make comparisons with existing data from age matched controls. We have collected aged match data from 84 control subjects and therefore do not need to recruit any further control subjects. The following Kinetic parameters will be defined by this analysis: number of subjects with bi-phasic sagittal moment pattern at the treated knee, maximum flexion and extension moments for both limbs (Nm), and maximum adduction and abduction moments (Nm).

The primary outcome measure for the study will be proportion of patients in each group with a bi-phasic sagittal knee moment pattern during gait. We will define a Biphasic gait as one in which a significant knee flexion and extension moment are generated during stance phase of gait. Our system reports Flexion moments with a positive value and Extension moments with a negative value. In order for a patient to be classified as having "Bi-phasic Gait", the patient must produce a moment pattern with both flexion (positive) and extension (negative) values – this can be assessed by looking at the maximum and minimum moment values and verifying that the maximum value has a positive value and minimum a negative value. Patterns that have either all positive or all negative max and min values will be defined as non-Bi-Phasic. Hence the decision as to whether a bi-phasic gait in stance exists will be produce without subjective inference from the researchers carrying out the test.

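### The one named check on missing primary outcomes assumes missing at random, so it cannot test drop-out caused by failure of the operated knee

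*Protocol*

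**What the plan says.** Section 11 (gait analysis) defines the primary endpoint by the signs of the largest and smallest knee moment in stance. Bi-phasic needs one positive and one negative value. The other class is also defined from a recorded curve: "Patterns that have either all positive or all negative max and min values will be defined as non-Bi-Phasic". Neither class mentions a patient who has no curve.

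Section 13 (revision of primary arthroplasty) keeps revised patients in follow-up but takes their data out of the overall analysis from the point of revision.

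Section 16 analyses the 1-year outcome by intention to treat, with a mixed effects logistic model adjusted for baseline gait. The only method it names for checking the effect of missing data is "most prominently using multiple imputation models exploring missing data mechanisms assumed to be generated under a 'missing at random' assumption".

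Section 15 plans for missing outcomes: "We will allow an additional 10% for loss to follow up at 1 year".

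**The concern.** Some 1-year walking tests may be missed because the operated knee has failed. Section 12.2.2 lists implant failure, revision, infection, periprosthetic fracture and pain among the anticipated events and, for the trial device or procedures, ligament or tendon damage and early loosening. Section 4 says that survivorship of non-robotic Bi-UCKA appears poorer than that of TKA. Knee-related loss could therefore be unequal between the arms and linked to the treatment under test.

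A likelihood-based logistic model fitted to observed outcomes rests on essentially the missing-at-random assumption. Imputation under the same assumption can use extra variables, but it does not test the assumption. If failed knees are missing because they failed, both analyses give them something close to the chance of success of patients who could be assessed. The check can then look reassuring whatever the reason for drop-out.

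A knee revised before 1 year has the same problem for another reason: section 13 removes its later data, while section 16 says patients are analysed as randomised.

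**Working it through.** **The plan's own figure.** Inputs from section 15: "23% of TKA patients have a bi-phasic gait after surgery compared to 70% of UKA patients"; "We therefore believe that 60% of Bi-UCKA patients might have a normal bi-phasic gait after surgery"; the comparison is made "with a power of 90% at a 5% level of significance using a chi-squared test". The significance level is taken as two-sided, which section 15 does not state. The formula without continuity correction, with p̄ = (0.23 + 0.60)/2 = 0.415, is

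n = [1.960·√(2·0.415·0.585) + 1.282·√(0.23·0.77 + 0.60·0.40)]² / 0.37²

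= (1.366 + 0.828)² / 0.1369 = 35.1, so 36 per group.

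This agrees with "we would need to study 36 patients per group". Allowing for 10% loss, 36/0.90 = 40 per group. The sample size is not in question. Planned loss is 40 − 36 = 4 per arm.

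**Size at the planning rates.** Take 60% and 23% as the rates among assessed patients, and let k of 40 in an arm be unassessable because of the knee. The protocol gives no value for k, so it is varied.

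- Imputation by arm alone leaves the difference at 60 − 23 = 37.0 points. Each missing Bi-UCKA patient is credited with 0.60 of a success and each missing TKA patient with 0.23.
- Counting these patients as not bi-phasic gives 60%·(40 − k)/40 and 23%·(40 − k)/40, with k set separately for each arm.

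| k, Bi-UCKA / TKA | Rates | Difference (points) | Overstatement (points) | Power, 40 per arm |
|---|---|---|---|---|
| 0 / 0 | 60.0% v 23.0% | 37.0 | 0 | 93.4% |
| 1 / 1 | 58.5% v 22.4% | 36.1 | 0.9 | 92.3% |
| 2 / 2 | 57.0% v 21.9% | 35.2 | 1.8 | 91.1% |
| 4 / 4 | 54.0% v 20.7% | 33.3 | 3.7 | 88.3% |
| 4 / 0 | 54.0% v 23.0% | 31.0 | 6.0 | 82.6% |
| 0 / 4 | 60.0% v 20.7% | 39.3 | −2.3 | 96.2% |

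**Effect on the conclusion.** These are uncorrected chi-squared tests, the test used in section 15. The counts are illustrative: 36 assessed per arm, with the 4 missing added back as stated.

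| Scenario | Near the planned effect | Smaller effect (25 points) |
|---|---|---|
| Assessed patients only | 22/36 v 8/36, p=0.0008 | 19/36 v 10/36, p=0.031 |
| 4 missing Bi-UCKA counted as failures, missing TKA left out | 22/40 v 8/36, p=0.004 | 19/40 v 10/36, p=0.077 |
| All 8 missing counted as failures | 22/40 v 8/40, p=0.001 | 19/40 v 10/40, p=0.036 |
| Bound: missing Bi-UCKA fail, missing TKA succeed | 22/40 v 12/40, p=0.024 | 19/40 v 14/40, p=0.26 |

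At the planned effect no row crosses 0.05. At the smaller effect, only the two rows that treat the arms unequally do.

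**The case against.** A reader might infer that the plan credits failed knees with successes and so puts the trial's conclusion at risk. The documents do not support that.

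- The credit is a fraction of a success, not a success. It could be smaller if the imputation model uses the 3-month scores, pain, function tests and complications scheduled in Table 1.
- The 10% in section 15 is loss for any reason. No section says how many tests would be missed because of the knee. A poor knee that can still walk is already classed, since a persistent flexion or extension pattern is not bi-phasic.
- The change to p=0.077 needs three things together: an effect of 25 points rather than 37, every Bi-UCKA loss caused by the knee, and no TKA loss so caused. The p=0.26 row is a bound, not a knee-failure scenario.
- Section 16 says the imputation is the most prominent method, not the only one, and defers to an analysis plan that is not shown and may contain more.

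A reader might also conclude that the primary endpoint itself should be redefined so that inability to walk counts as failure. That is debatable in a trial described as explanatory, where the endpoint is biomechanical. It would also come late: section 21 has 1-year data collection ending in July 2019, and the current protocol version is dated March 2021.

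These points limit the size and change the remedy. They do not change the fact that the one method named cannot examine the most obvious way in which missing outcomes could mislead, or that sections 13 and 16 disagree about revised knees.

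**Conclusion.** The concern holds in a limited form. The named robustness check shares the assumption of the model it is meant to check. Patients with no curve because of the operated knee have no place in the endpoint definition. Removing knees revised before 1 year conflicts with intention to treat.

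At the planning rates with the full 10% loss attributed to the knee, the difference is overstated by 3.7 points if losses are balanced and by 6.0 if they fall only in the Bi-UCKA arm. If they fall only in the TKA arm it is understated by 2.3. With one or two per arm the overstatement is about 1 to 2 points. The planned effect survives every scenario tried; a 25-point effect does not if losses are concentrated in the Bi-UCKA arm.

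These figures assume the number of knee-related missing tests, imputation by arm alone, and a simple chi-squared test in place of the adjusted mixed model. The point merits a change because the remedy is cheap, not because the result is shown to be fragile.

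**What to change.** 1. In section 16, keep the missing-at-random imputation and add a pre-specified sensitivity analysis that departs from it. Vary the chance of success for missing outcomes separately by arm, up to best and worst case, and report the point at which the conclusion changes.
2. Include one scenario that counts as not bi-phasic any patient who could not do the 1-year walk because of the operated knee, or whose knee was revised before 1 year. Use the withdrawal reasons, complications and revision details that sections 11 and 13 already collect, classified by someone unaware of allocation. Leave the primary endpoint definition as it is.
3. Reconcile the removal of revised patients in section 13 with the intention-to-treat statement in section 16, for the primary outcome in particular.

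The cost is a short extra analysis, a blinded review of existing records and some wording. The Bi-UCKA rate may look slightly less favourable in that sensitivity analysis. If the 1-year analysis has already been run, the addition should be reported as made afterwards.
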